JRMO	Joint Research Management Office
NHS REC	National Health Service Research Ethics Committee
NHS R&D	National Health Service Research & Development
Participant	An individual who takes part in a clinical trial
PBMC	Peripheral blood mononuclear cells
PI	Principal Investigator
PIS	Participant Information Sheet
QMUL	Queen Mary University of London
REC	Research Ethics Committee
ROC	Receiver Operating Characteristic
SAE	Serious Adverse Event

[figure not shown]
3. Signature page

Chief Investigator Agreement

The study, as detailed within this Research Protocol, will be conducted in accordance with the principles of Good Clinical Practice, the UK Policy Framework for Health and Social Care Research, and the Declaration of Helsinki and any other applicable regulations. I agree to take responsibility for the statistical analysis and oversight of this study.

Chief Investigator Name: [name]

Signature:

Date: 20th June 2022

4. Summary and synopsis

Short title	IDentification of EGPA Autoantigens (IDEA)
Methodology	Laboratory-based research study using blood and sputum samples from healthy controls and patients with EGPA, Severe Eosinophilic Asthma and other eosinophilic diseases.
Objectives / aims	To determine the presence, or not, of auto-antibodies to self-peptides in severe eosinophilic asthma and EGPA.
Number of participants	120 participants (90 patients and 30 healthy controls)
Inclusion and exclusion criteria	
Major Inclusion Criteria:
 
Patients: Patients with Severe Eosinophilic Asthma and/or EGPA and/or eosinophilic COPD and/or eosinophilic oesophagitis, age 18 yo and over, and able to give consent.
 
Healthy Controls: age 18 yo and over, and able to give consent.
 
Exclusion criteria:
 
Pregnancy; anaemia; rituximab, plasmapheresis or IVIG infusion ever

Study duration	30 months (18 months recruitment)

5. Introduction

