Previous research at our centre and with collaborators has shown that post-translational modification of potential auto-antigens is a key step in breaking self-tolerance and development of autoimmune disease (Ryan, Nissim et al. 2014) (Eggleton, Nissim et al. 2013). For example we have shown auto-antibodies to oxidised type II collagen are much more frequent than those to native type II collagen in rheumatoid arthritis (Nissim, Winyard et al. 2005). Similarly in type 1 diabetes mellitus auto-antibodies to insulin that has undergone oxidative post-translational modification are significantly more common than those to native insulin (Strollo, Vinci et al. 2015).

Oxidative stress, implicated in the formation of oxidised auto-antigens, is a major feature of uncontrolled asthma inflammation (Mak, Ho et al. 2013). However, to date the potential role of modified auto-antigens in the airways has not been studied in severe eosinophilic asthma, EGPA and other related diseases.

In this project we will look for auto-antibodies to relevant proteins both in native form and importantly in post-translationally modified forms. Potential modified auto-antigens are eosinophil proteins (analogous to the cytoplasmic neutrophil proteins identified in vasculitides such as Granulomatosis with Polyangiitis (formerly known as Wegener's) and alternatively structural proteins such as collagen V. As well as advancing our understanding of asthma pathology, identifying a serum auto-antibody that could then be used as a clinical blood test, analogous to anti-CCP antibodies in rheumatoid arthritis, may revolutionise diagnosis of severe eosinophilic asthma and EGPA. There is a considerable burden of undiagnosed severe eosinophilic asthma in part due to difficulties in definitive diagnosis and a diagnostic blood test would help diagnose these patients, allowing them to receive necessary treatment.

We have previous experience of identifying novel autoantigens in Systemic Lupus Erythematosus (SLE) (Lewis et al. 2018), using an advanced protein microarray developed by Oxford Gene Technology, now known as Sengenics. This protein microarray technology benefits from using correctly folded proteins with preserved native epitopes, and the technology permits on chip modification of proteins such as citrullination or oxidation.

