6.1. Study Outcomes / Endpoints

Primary objectives

- The presence of serum and/or sputum auto-antibodies to eosinophil and/or basement membrane proteins will be established in severe eosinophilic asthma and EGPA cohorts, and patients with other asthma phenotypes and related eosinophilic diseases.
- Whether auto-antibodies to post-translationally modified self-antigens are more prevalent than to native self-antigens will be examined, and which post-translational

modifications are important to be studied (including particulate matter air pollution as a potential combined stimulus of eosinophil activation and protein modification).

Primary outcomes

- Correlations of auto-antibodies to clinical variables such as spirometry (FEV1 % predicted), pattern of organ involvement, age of onset, requirement for maintenance of oral corticosteroids, eosinophil count, highest recorded eosinophil count and FeNO will be studied.
- Predictive ability to diagnose severe eosinophilic asthma / EGPA of relevant auto-antibodies will be examined by ROC AUC analysis.

Secondary outcomes

- Exploratory Outcomes: Further experimental assays may be conducted to examine immunological mechanisms underpinning associations of auto-antibodies to disease.

7. Study population

90 patients under the care of the Barts Health NHS Trust and Royal Free London NHS Trust with severe eosinophilic asthma, EGPA, eosinophilic COPD and other related pathologies will be recruited.

At least 60 patients will have severe eosinophilic asthma and/or EGPA, and will be recruited from the regional North Central and East London Severe Asthma Service, the Royal Free London NHS Trust and from the Barts Arthritis Centre, with multi-disciplinary consensus diagnoses of severe eosinophilic asthma and/or EGPA respectively. Patients will be phenotyped with blood leucocyte differential, lung function tests and FeNO as appropriate in conjunction with detailed medical history.

Up to a further 30 patients with milder asthma, other vasculitides, eosinophilic COPD, and/or eosinophilic oesophagitis will be recruited from other clinics at Barts Health NHS Trust and the Royal Free London NHS Trust.

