7.2. Exclusion criteria

- *Any inclusion criteria not met*
- *Known Pregnancy*
- *Anaemia*
- *Donation of more than 240mls blood in the last sixteen weeks (four months) to any other research study or as a donation to the National Blood Transfusion Service*
- *Rituximab, plasmapharesis or polyclonal immunoglobulin infusion (ever)*

8. Study design

Study Visit (Patients)

This is a single study visit encompassing patient recruitment, consent, data collection and provision of a peripheral blood sample with/without concurrent sputum sample, with no follow-up visits.

Patients will be recruited via Outpatient Clinics conducted at St Bartholomew's (Bart's) Hospital, The Royal London Hospital, and Mile End Hospital (all Bart's Health NHS Trust), Royal Free London NHS Trust, as well as from inpatients at these hospitals under the care of the Respiratory Medicine and Rheumatology teams (including those under other services needing inpatient respiratory medicine or rheumatology review).

Potential patients will be identified by their clinical team and invited to participate. If interested they will be given a Participant Information Sheet (PIS). Informed Consent and Screening will be undertaken by a GCP-trained member of the clinical team or GCP-trained researcher. An anonymised data collection case report form (CRF) will be completed by a member of the clinical team and a linked (anonymised) blood sample collected by a staff member trained in phlebotomy. If the patient is able to spontaneously produce sputum, and there is no clinical concern about TB infection, then they will be asked to cough a sample in to a sterile sample pot.

The linked anonymised CRF and samples will then be taken to the research laboratories at QMUL for immune cell analysis. Laboratory immunology studies will be conducted by as per protocol (Section 14) by a dedicated Post-Doctoral Research Assistant.

Study Visit (Healthy Controls)

There is a single study visit encompassing healthy control recruitment, consent, data collection and taking of blood sample, with no follow-up visits.

Healthy controls will be recruited at QMUL, Bart's Health and Royal Free sites via poster advertisement.

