13.2. Source data

Case Report Form (Patients) data variable list:

1. Age
2. Gender
3. Ethnicity (optional)
4. Occupational history
5. Confirmation participant meets Inclusion and Exclusion criteria (Yes/No)
6. Smoking history
7. Diagnosed medical condition(s) and basis for diagnoses with focus on diagnostic criteria for Severe Eosinophilic Asthma, EGPA
8. Suspected medical conditions(s)
9. Immunosuppressive medication(s) dose regimes and history
10. Previous treatment history, especially corticosteroid history
11. Full blood count (haematology)
12. Most recent and previous FeNO breath tests, if done
13. Auto-immune serology results
14. Spirometry and gas transfer tests, if done
15. Highest previous blood eosinophil count, ANCA serology (immunofluorescence, anti-PR3 and anti-MPO antibody titre) and trend
16. Investigations for target organ involvement in patients with suspected vasculitis including histology
17. Clinical disease activity measures (for example Birmingham Vasculitis Activity Score (BVAS), Asthma Control Questionnaire (ACQ)-6)

Case Report Form (Healthy Control) data variable list:

1. Age
2. Gender
3. Ethnicity (optional)
4. Occupational history
5. Confirmation participant meets Inclusion and Exclusion criteria (Yes/No)
6. Smoking history

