Eosinophil proteins such as those previously identified as of importance (e.g. eosinophil-peroxidase, *EPX*) and also novel candidate proteins specific to eosinophils (including *ARFIP1*, *BCL2A1*, *PPCDC*, *SLC12A6* etc) as identified by FANTOM5 geneset analysis will be purchased or synthesised in Expi-293 cells, by obtaining tagged clones from Origene and developing stable expressing cell lines. Protein synthesis be confirmed by western blot. Proteins will be used to coat ELISA plates with/without prior post-translational modification. Presence of donor serum antibodies in serum and in sputum will then be examined by ELISA using appropriate enzyme-

linked secondary antibodies. Similar extracellular matrix proteins such as collagen V will be investigated.

POST-TRANSLATIONAL MODIFICATION OF PEPTIDES

Eosinophil suspensions / slides and commercially sourced / synthesised target proteins (e.g. eosinophil peroxidase and collagen V) will be modified as follows:

Oxidative modification – by hydroxyl radical exposure with hypochlorous acid using our established methodology (Strollo, Vinci et al. 2015). Citrullination – by recombinant peptidylarginine deiminase (PAD).

Ambient pollutants and nanopollutants are known to be able to induce both oxidative stress and protein citrullination as well as potentially direct eosinophil activation. Given the known association between asthma and ambient pollution we will additionally examine potential serum antibodies to ambient pollution particulate matter stimulated/modified eosinophil and collagen proteins.

- Samples may also be analysed to address associated Exploratory Outcomes, to examine immunological mechanisms underpinning auto-antibody disease associations. Applicable experimental techniques to include:

Blood and sputum leukocyte phenotyping *ex vivo* by flow-cytometry (FACS) analysis of circulating immune cell subsets (including myeloid-lineage cells, conventional/unconventional lymphocyte populations, and granulocyte populations).

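### Patients with a second autoimmune disease can enter the case group, and no planned analysis shows whether the results for oxidised and citrullinated antigens depend on them

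*Combined protocol and SAP*

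**What the plan says.** **Who can be a case.** The synopsis (Section 4) plans "120 participants (90 patients and 30 healthy controls"). Section 7 states that "At least 60 patients will have severe eosinophilic asthma and/or EGPA". Recruitment sources include patients "from the Barts Arthritis Centre, with multi-disciplinary consensus diagnoses of severe eosinophilic asthma and/or EGPA respectively". Section 8 adds inpatients "under the care of the Respiratory Medicine and Rheumatology teams". Sections 7.1 and 7.2 contain no exclusion for a second autoimmune disease in patients. The nearest criterion is by treatment: any previous rituximab, plasma exchange or immunoglobulin infusion.

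**Who can be a control.** Section 7.1 rules out vasculitis, chronic respiratory disease, allergy, infection and systemic immunosuppressants. It does not name rheumatoid arthritis or type 1 diabetes.

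**What is tested.** Section 14 exposes eosinophils and target proteins to oxidation and to citrullination ("by recombinant peptidylarginine deiminase (PAD"), and tests the ELISA proteins with and without modification. Section 5.1 gives as precedent that "auto-antibodies to oxidised type II collagen are much more frequent than those to native type II collagen in rheumatoid arthritis", makes the same point for oxidised insulin in type 1 diabetes, and takes anti-CCP in rheumatoid arthritis as its model for a blood test.

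**What is analysed.** Section 6.1 makes the prevalence of antibodies to modified versus native antigens a primary objective and ROC AUC a primary outcome. The covariates in Section 6 are disease length, atopy, nasal polyps, gender and age. Section 10.2 names parametric and non-parametric tests, linear regression and ROC analysis, and no sensitivity analysis. For patients, the CRF (Section 13.2) records "Diagnosed medical condition(s) and basis for diagnoses" as item 7 and auto-immune serology as item 13. The healthy-control CRF has neither item.

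**The concern.** The protocol's own background describes antibodies to modified self-proteins in diseases other than the ones under study. If some cases also have such a disease, part of the signal on a modified eosinophil protein or on modified collagen V could come from that disease.

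The comparison that looks like a safeguard is not one. Suppose a patient's serum reacts to a modification whatever protein carries it. That patient is positive on the modified form and negative on the native form, exactly as a patient with a true antibody to the modified eosinophil antigen would be. The contrast counts both in the same cell.

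At stake are three results: the prevalence of antibodies to modified antigens, the modified-versus-native comparison, and to a lesser degree the ROC AUC. Section 5.1 looks towards a diagnostic blood test, Section 7 intends replication of positive findings, and Section 10.1 will use these data to size later studies. A non-specific finding would carry into all three.

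**Working it through.** **1. The plan's own figures.** 60 + 30 = 90 patients and 90 + 30 = 120 participants, so the counts agree. Section 10.1 makes no power calculation, and no alpha, effect size or comorbidity rate is stated, so there is no further figure to reproduce. What follows is illustration.

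**2. Inputs.**
- From the documents: 60 cases (the stated minimum) and 30 controls.
- Assumed: *f*, the share of cases with a second autoimmune disease (5%, 10%, 20%); *q*, the share of those who react to the modified form only (50%, 70%); a 5% background positivity *b* in step 4; no affected controls; no antibody specific to asthma or EGPA; a two-sided 5% level. The plan names no test for paired positivity; I use the exact McNemar (sign) test.

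**3. Modified versus native, paired in 60 cases.** If *k* patients are positive on the modified form only and none the other way, p = 2 × (1/2)^k.
- k = 5: 2/32 = 0.063
- k = 6: 2/64 = 0.031

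So 6 of 60 (10%) is enough. With no other discordance, the number of such patients is binomial (60, *f* × *q*).

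| f | q | Expected modified-only positives (60 × f × q) | Chance of 6 or more |
|---|---|---|---|
| 5% | 50% | 1.5 | 0.004 |
| 5% | 70% | 2.1 | 0.018 |
| 10% | 50% | 3.0 | 0.079 |
| 10% | 70% | 4.2 | 0.242 |
| 20% | 50% | 6.0 | 0.563 |
| 20% | 70% | 8.4 | 0.862 |

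**4. Cases versus 30 controls, q = 70%.** Apparent case prevalence = f·q + (1 − f)·b. For a positive/negative marker, AUC = 0.5 + (case prevalence − control prevalence)/2. The last column uses the normal-approximation formula for two proportions.

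| f | Apparent case prevalence | AUC | Chance of p < 0.05 |
|---|---|---|---|
| 5% | 0.035 + 0.0475 = 8.2% | 0.516 | 0.07 |
| 10% | 0.070 + 0.045 = 11.5% | 0.532 | 0.14 |
| 20% | 0.140 + 0.040 = 18.0% | 0.565 | 0.37 |

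With 0 of 30 controls positive, 8 positive cases are needed for Fisher p < 0.05 (p = 0.048; 7 cases give 0.090).

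**5. Continuous marker.** If affected patients are shifted upward by an assumed 2 SD, AUC = 0.5(1 − f) + f × Φ(2/√2), with Φ(1.414) = 0.921. This gives 0.542 at 10% and 0.584 at 20%.

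**The case against.** **The documents do not show that such patients are enrolled.** A reader might infer from the arthritis-centre and inpatient routes ("as well as from inpatients at these hospitals under the care of the Respiratory Medicine and Rheumatology teams") that the case group will contain many patients with rheumatoid arthritis or lupus. The text does not support that. Section 7 requires a consensus diagnosis of severe eosinophilic asthma and/or EGPA, and rheumatology is a natural source of EGPA. Such patients can enter; how many do is unknown. This stands.

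**The mechanism is an extrapolation.** Section 5.1 concerns named antigens in named diseases. It does not say that those sera bind citrullinated or oxidised proteins in general, or eosinophil proteins in particular. This stands, and it is why *q* is an assumption. The possibility remains open, and nothing planned would detect it directly.

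**There are partial safeguards.** Section 6 plans correlations with other auto-antibodies and three serology-defined subsets. Sections 7 and 7.1 admit GPA and other vasculitides. Section 14 uses several candidate proteins, so reactivity to a modification alone would tend to appear across the panel. These all have value. None, however, recalculates prevalence, modified versus native, or the AUC without the patients in question. The subsets are there to find novel antibodies; there is no rheumatoid arthritis, lupus or type 1 diabetes comparator; and every protein on the panel is itself a candidate.

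**The direction is not fixed for case-control results.** One might conclude that every estimate is pushed up on the case side. But a control with rheumatoid arthritis or type 1 diabetes who takes no systemic immunosuppressant is also eligible, and the control CRF would not record it. The figures in step 4 assume no affected controls. The paired comparison in step 3 uses cases only and is not affected by this.

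**Excluding on serology could do harm.** Removing patients positive for anti-CCP or similar selects on a variable related to the outcome: if asthma or EGPA patients truly make anti-citrulline antibodies, it deletes the signal. It could also cut into the ANA-positive subset that Section 6 sets out to study, and anti-CCP is not named on the CRF. This stands and shapes the fix.

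**Conclusion.** The gap is real but limited. A second autoimmune disease is permitted in cases, the antigens carry modifications that the protocol's background connects with other autoimmune diseases, and no planned analysis shows whether the modified-antigen results depend on such patients. The modified-versus-native contrast cannot separate general reactivity to a modification from reactivity to the eosinophil or collagen antigen.

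The size depends on comorbidity and reactivity rates that the documents do not give. At about 5% comorbidity the effect is negligible. At 10–20% with high reactivity it is material for modified versus native: the chance of a spurious significant result is 0.24 to 0.86 at 70% reactivity. The AUC effect is modest across the range: at most 0.565 for a positive/negative marker, or 0.584 under the 2 SD shift.

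It does not follow that an antibody found in this study would be non-specific, or that the case group is known to be contaminated. What follows is that the plan as written could not tell. In a pilot meant to generate associations, that makes this a cheap improvement worth adopting. It changes no sample-size figure.

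**What to change.** 1. **Section 10.2:** state that the prevalence, modified-versus-native and ROC analyses will be reported with and without participants who have another diagnosed autoimmune disease. Define this by recorded diagnosis (patient CRF item 7), not by serology. Call it a sensitivity analysis, not a condition that an antibody must pass.
2. **Section 13.2:** record the same diagnoses on the healthy-control CRF, so that the rule applies to both groups.
3. **Section 14, target protein assays:** on modified ELISA plates include one unrelated protein modified in the same way, and report its signal beside the targets before any antibody is called antigen-specific. Subtracting that signal need not be mandatory.

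**Cost:** one extra analysis with somewhat fewer patients (at 10% comorbidity 54 of 60 remain; at 20%, 48), one extra item on the control CRF, and a few wells per plate. No extra participants, samples or visits are needed.

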14.1. Study Workflow

Blood samples will be collected in up to 4 Serum Separator Tube (SST) vacutainer tubes and up to 4 Acid Citrate Dextrose (ACD) vacutainer tubes.

Serum samples from SST tubes will be aliquoted and stored at -80°C pending analyses as above.

Peripheral blood samples from ACD tubes will be used to store peripheral blood mononuclear cells (PBMC) (with/without sorting of eosinophils and/or other cell subsets such as neutrophils prior to freezing) as viably-frozen cells in freezing medium or in RNA preservation buffer.

Sputum will be processed to isolate sputum plugs from saliva contamination, diluted with buffered saline before centrifugation to separate supernatant and cellular components. Aliquots of supernatant will be stored at -80°C pending analyses as above. The cellular fraction will be treated with dithiothreitol, filtered and final cell suspension stored at -80°C for further analysis or in RNA preservation buffer.

15. Safety reporting

The only patient contact in this study is the consent process and the sample donation (venipuncture and collection of blood into sterile containers using standard phlebotomy practice at the recruiting NHS Trust, with/without collection of spontaneously produced sputum). As such Adverse Events (AE) and Serious Adverse Events (SAE) are extremely unlikely. In the event of an AE or SAE then this will be reported to the CI by any research team members, and escalated as appropriate by the CI.

Notification and Reporting of Serious Adverse Events

Serious Adverse Event (SAEs) that are considered to be 'related' and 'unexpected' will be reported to the sponsor within 24 hours of learning of the event and to the Main REC within 15 days in line with the required timeframe.

16. Monitoring and auditing

The Sponsor or delegate retains the right to audit any study, study site or central facility. In addition, any part of the study may be audited by the funders where applicable.

As this is exploratory laboratory research, no formal monitoring plan is planned.

17. Study committees

There is no trial committee for this study. Members of the research team are as follows:

Chief Investigator (CI)	[name] Senior Clinical Lecturer and Consultant Rheumatologist, William Harvey Research Institute, Queen Mary University of London, UK
Co-Investigator	[name] [name] Consultant Respiratory Physician and Hon Senior Lecturer, Barts Health NHS Trust and Queen Mary University of London, UK
